9.4.3 Handling of missing values/censoring/discontinuations

Imputation of incomplete adverse events start and end dates will follow standard conventions and will be described in detail in the statistical analysis plan.

9.4.4 Sensitivity analyses

No sensitivity analyses are planned for the assessment of the primary variables.

9.5 Analysis of secondary variables

9.5.1 Efficacy variables

An overview of the secondary efficacy variables and planned analysis is given in [Table 9-2](#).

Table 9-2 Secondary efficacy variables and analyses

Variable	Analysis
At least a one point improvement of fibrosis	Cochran-Mantel-Haenszel test controlling for baseline fibrosis stage for each tropifexor + CVC combination vs. each monotherapy treatment, with supporting information from risk differences, odds ratios with 95% confidence intervals
Resolution of steatohepatitis (as determined by central pathologist)	Cochran-Mantel-Haenszel controlling for baseline fibrosis stage for each tropifexor + CVC combination vs. each monotherapy treatment, with supporting information from risk differences, odds ratios with 95% confidence intervals

There is a single secondary objective in this study which is to characterize the efficacy of tropifexor + CVC in patients with NASH with fibrosis stage F2/F3 as assessed by histological improvement after 48 weeks of treatment compared to monotherapies (tropifexor and CVC) relative to baseline biopsy. There are two estimands that will be used to evaluate this objective.

The first estimand is the difference on the proportion of patients on the different tropifexor + CVC regimens who achieve at least a one point improvement in fibrosis at Week 48 compared to tropifexor and CVC monotherapy patients. It is assumed that anyone who does not have a Week 48 liver biopsy or does not remain on their randomized study treatment for at least 24 weeks (even if a Week 48 biopsy was obtained) will have their outcome imputed by multiple imputation (MI). For subjects who remain on their randomized study treatment for at least 24 weeks, but discontinue study treatment prior to Week 48, available Week 48 biopsy results will be used as observed. This is a hypothetical strategy addressing the question “what would be the outcome if subjects had stayed at least 24 weeks on treatment and a Week 48 biopsy had been obtained”. Treatment differences between tropifexor + CVC combination therapy and monotherapy with tropifexor or CVC will be evaluated using a Cochran-Mantel-Haenszel test controlling for baseline fibrosis stage (F2/F3). The estimand will be evaluated in the FAS population.

The second estimand is the difference in the proportion of patients on the different tropifexor + CVC regimens who achieve resolution of steatohepatitis at Week 48 relative to baseline compared to tropifexor and CVC monotherapy patients. It is assumed that anyone who does not have a Week 48 liver biopsy result or does not remain on their randomized study treatment for at least 24 weeks will have their outcome imputed by multiple imputation (MI). The handling of intercurrent events (discontinuation of assigned treatment) is equivalent to the first estimand as described above. Treatment differences between tropifexor + CVC combination therapy and monotherapy with tropifexor or CVC will be evaluated using a Cochran-Mantel-

Haenszel test controlling for baseline fibrosis stage (F2/F3). The estimand will be evaluated in the FAS population.

Due to COVID-19 pandemic, it may not be possible for patients to return on time for Week 48 visit to perform liver biopsy and according to drug dispensing plan in [Section 5.5.2](#), the Week 48 liver biopsy can be delayed by approximately 10 weeks. Since the purpose of the secondary efficacy analysis is to evaluate the potential histological benefit of study treatment, all biopsies obtained, including those from eligible patients after week 48, will be included in the analysis.

Sensitivity analyses:

Sensitivity analyses will be conducted to account for delayed Week 48 biopsies due to extended treatment under COVID-19 pandemic. Further details are to be described in the statistical analysis plan (SAP).

9.5.2 Safety variables

All safety variables (i.e. adverse events, laboratory data, vital signs, and ECG) will be summarized by treatment for all patients of the safety set. Safety variables which are part of the primary variables are listed in [Table 9-1](#) as well. Analyses of the safety variables will be performed in the Safety Set.

9.5.2.1 Adverse events

Treatment emergent adverse events (events started after the first dose of study treatment or events present prior to the first dose of study treatment but increased in severity based on preferred term) will be summarized. AEs will be summarized by presenting, for each treatment group, the number and percentage of patients having experienced

- Any adverse event (AE),
- Any serious adverse event (SAE),
- Any adverse event by primary system organ class (SOC),
- Any adverse event by preferred term,
- Any adverse by severity,
- Any adverse event possibly related to study treatment (investigator assessment),
- Any adverse event resulting in discontinuation of study treatment,
- Any adverse events of special interest for tropifexor or CVC treatment.

Exposure adjusted tabulations of adverse events and tabulations of appropriate adverse events according to defined intervals will be provided as well. If a patient reported more than one adverse event with the same preferred term, the adverse event with the greatest severity will be presented. If a patient reported more than one adverse event within the same primary system organ class, the patient will be counted only once with the greatest severity at the system organ class level, where applicable. A separate summary will be provided for deaths, if they occur during the course of the study.

9.5.2.2 Laboratory data

The summary of safety laboratory evaluations will be presented for the groups of laboratory tests (e.g. hematology, clinical chemistry). Descriptive summary statistics for the change from baseline to each study visit will be presented. These descriptive summaries will be presented by test group, laboratory test and treatment group. Change from baseline will only be summarized for patients with both baseline and post baseline values. Relative and absolute frequencies of patients with liver events as defined in [Appendix 2](#) will also be provided, as well as shift tables based on the normal laboratory ranges. For the shift tables, the normal laboratory ranges will be used to evaluate whether a particular laboratory test value was normal, low, or high for each visit value relative to whether or not the baseline value was normal, low, or high. These summaries will be presented by laboratory test category and treatment group.

The number and percentage of patients with clinically notable laboratory results after baseline will be presented. Clinically notable laboratory results, for those parameters where ranges are available. Only patients with laboratory results within the normal reference range from the central laboratory at baseline will be included in the tabulations.

Safety laboratory parameters which are also part of the efficacy analyses will be included in the safety tables as well (e.g. liver enzymes, lipids).

9.5.2.3 Baseline definition

Generally, baseline is defined as the last assessment before date and time of first administration of study drug; if only the date is available, the last assessment before or at the date of first administration of study drug will be used. For transaminases (ALT, AST, GGT) and bilirubin, the baseline value will be calculated as the mean of the last two assessments before first administration of the study drug, which are usually those taken at the Screening 2 and Baseline visit (if a test was performed).

9.5.2.4 Vital signs

Analysis of the vital sign measurements using summary statistics for the change from baseline for each post-baseline visit will be performed. These descriptive summaries will be presented by vital sign and treatment group. Change from baseline will only be summarized for patients with both baseline and post-baseline values. Patients with notable vital signs as defined in [Appendix 1](#) will be listed.

[figure not shown]
9.5.2.5 ECG

[figure not shown]
ECG data will be summarized by treatment and visit (post-baseline ECGs are performed at Week 24 and Week 48).

[figure not shown]
The Fridericia QT correction formula (QTcF) will be used for clinical decisions and for analyses. Notable QTcF values and changes from baseline will be summarized at Week 24 and Week 48. A notable value is defined as a QTcF interval of greater than 450 ms. The categories used for the change (increase) in QTcF are: ≤ 30 ms, > 30 to ≤ 60 ms and > 60 ms.

9.5.3 Resource utilization

Data relating to resource utilization will be used for the purpose of economic evaluation which will be carried out and reported as a separate activity.

9.7 Interim analyses

No interim analysis is planned for the study.

9.8 Sample size calculation

The primary objective of the study is to determine if there is a safe combination between one of the chosen doses of tropifexor and 150 mg of cenicriviroc. However, the assessment will be made based on the whole safety profile and not on quantitatively formulated hypotheses for distinct parameters. Therefore the sample size is based on the feasibility with respect to expected speed of enrollment and duration of the study, not on formal statistical criteria.

[figure not shown]
9.8.1 Power considerations with given sample size for safety assessment

Events with a true incidence of 30% and above are likely to be observed (almost 100% probability) in a group of 50 patients (size of each treatment group). Events with true incidences below 10% down to 3% are still very likely to be observed, while events are observed with less

[figure not shown]
than 50% probability only if the true incidence is less than about 2.5% (Figure 9-1). It is noteworthy, however, that a single patient constitutes 2% in a sample of 50.

Figure 9-1 Binomial probability to observe an event with given sample size

Probabilities of the incidence being below a certain threshold are plotted in Figure 9-2 for a sample size of 50 patients when the event is observed in 0, 1, 2, ...,10 patients (assuming a beta distribution with prior shape parameters 0.33, 0.33).

Figure 9-2 Predictions for probability of event based on observed number

For example, if 0 events are observed, the probability (Prob) that the incidence is $\leq 5\%$ would be 98.7%. If an event is observed in one patient, the probability that the incidence is $\leq 5\%$ would be 86.6%. Similarly, if an event is observed in 10 patients (one fifth), the probability that the incidence is $\leq 20\%$ would be approximately 50% (calculated using R function pbeta).

9.8.2 Power considerations with given sample size for efficacy assessment

To evaluate the effectiveness of tropifexor + CVC with respect to the proportion of patients who have at least a one point improvement in fibrosis at Week 48 compared to baseline (i.e, the response rate), one needs to consider the effect size that one is able to detect with respect to both tropifexor and CVC as monotherapy.

- For CVC, based on information from the CENTAUR Phase 2b study, [Friedman 2017](#)), it can be assumed that the monotherapy response rate at Week 48 in F2/F3 patients would be approximately 35%
- For tropifexor, a response rate of 42% is assumed (best-case scenario) based on the interpolation of expected Week 72 response rate and assuming linear improvement over time
- For the combined effect of tropifexor + CVC it will be assumed that 75% of the efficacy for CVC will be added to the effect of tropifexor (i.e. a response rate of 69%)

For comparisons between tropifexor + CVC and CVC monotherapy a 2-group continuity corrected χ^2 test of proportions with type error 0.10 (2-sided, no adjustment for multiple comparisons), a sample size of 50 per group results in a power of 95% (nQuery Advisor 7.0).

For comparisons between tropifexor + CVC and tropifexor monotherapy a 2-group continuity corrected χ^2 test of proportions with type error 0.10 (2-sided, no adjustment for multiple comparisons), a sample size of 50 per group results in a power of 81% (nQuery Advisor 7.0).

Further scenarios assuming different response rates for tropifexor and the magnitude of effect added to tropifexor by CVC are described in [Table 9-4](#).

Table 9-4 Power for detecting a treatment difference between tropifexor + CVC and tropifexor and CVC monotherapy

Assumed tropifexor response rate	Assumed response rate of tropifexor + CVC	Power N = 50/arm vs. tropifexor monotherapy	Power N = 50/arm vs. CVC monotherapy
Current target 42% response rate at Week 48 (50% improvement over OCA)	½ effect of CVC added to tropifexor ((60%)	48%	75%
	¾ effect of CVC added to tropifexor (69%)	81%	95%
	Full effect of CVC added to tropifexor (77%)	96%	99%
Response rate between target and OCA at Week 48 (35%)	½ effect of CVC added to tropifexor (53%)	48%	48%
	¾ effect of CVC added to tropifexor (62%)	81%	81%
	Full effect of CVC added to tropifexor (70%)	96%	96%
Worst case: tropifexor same effect as OCA 28% at Week 48	½ effect of CVC added to tropifexor (46%)	50%	23%
	¾ effect of CVC added to tropifexor (55%)	82%	56%
	Full effect of CVC added to tropifexor (63%)	96%	81%

*Power calculated assuming a two-sided Type I error rate of 0.10

10 Ethical considerations

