Study 652-2-203 (CENTAUR) is a 2-year placebo-controlled Phase 2b study in 289 adult participants with liver fibrosis and NASH. Enrollment completed in June 2015 and Year 2 database lock was performed on 22 August 2017. In CENTAUR, the Year 1 primary endpoint of NAFLD Activity Score (NAS) improvement by at least 2 points (and no worsening of fibrosis) in the intent-to-treat (ITT) population and the key secondary endpoint of resolution of steatohepatitis (and no worsening of fibrosis) was achieved in a similar proportion of subjects on CVC (N = 145) and placebo (N = 144) (16% vs 19%, $p = 0.52$ and 8% vs 6%, $p = 0.49$, respectively). However, the fibrosis endpoint (i.e., improvement in fibrosis by at least 1 stage and no worsening of steatohepatitis) was met in twice as many subjects on CVC than placebo in the ITT population (20% vs 10%; $p = 0.02$). At Year 1, a higher proportion of participants in the CVC group (29%) compared with the combined placebo group (19%) had an improvement of at least 1 stage at Year 1 per the NASH CRN staging system. Similarly, a higher proportion of participants in the CVC group (35%) compared with the combined

placebo group (22%) had an improvement of at least 1 stage at Year 1 per the Ishak fibrosis staging system. Treatment benefits were greater in those with higher disease activity and fibrosis stage at baseline. Biomarkers of systemic inflammation were reduced with CVC. In summary, CVC showed a clinically meaningful antifibrotic benefit and anti-inflammatory activity in NASH patients with liver fibrosis.

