1.2 Purpose

[figure not shown]
The purpose of this study is to assess the safety, tolerability, efficacy [REDACTED] of two regimens of tropifexor and cenicriviroc (CVC) (further described as tropifexor + CVC) compared to monotherapies tropifexor and CVC in patients with NASH and liver fibrosis. Data from this study will be used to evaluate whether further development of combination therapy with tropifexor + CVC in the treatment of patients with non-alcoholic steatohepatitis (NASH) and liver fibrosis is beneficial.

[figure not shown]
2 Study objectives and endpoints

[figure not shown]

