### 3.2 Power considerations with given sample size for efficacy assessment

To evaluate the effectiveness of tropifexor + CVC with respect to the proportion of patients who have at least a one point improvement in fibrosis at Week 48 compared to baseline (i.e, the response rate), one needs to consider the effect size that one is able to detect with respect to both tropifexor and CVC as monotherapy.

- For CVC, based on information from the CENTAUR Phase 2b study, Friedman (2017), it can be assumed that the monotherapy response rate at Week 48 in F2/F3 patients would be approximately 35%
- For tropifexor, a response rate of 42% is assumed (best-case scenario) based on the interpolation of expected Week 72 response rate and assuming linear improvement over time
- For the combined effect of tropifexor + CVC it will be assumed that 75% of the efficacy for CVC will be added to the effect of tropifexor (i.e. a response rate of  $42 + 0.75 \cdot 35 = 69\%$ )

For comparisons between tropifexor + CVC and CVC monotherapy a 2-group continuity corrected  $\chi^2$  test of proportions with type I error rate of 0.10 (2-sided, no adjustment for multiple comparisons), a sample size of 50 per group results in a power of 95% (nQuery Advisor 7.0).

For comparisons between tropifexor + CVC and tropifexor monotherapy a 2-group continuity corrected  $\chi^2$  test of proportions with type I error rate of 0.10 (2-sided, no adjustment for multiple comparisons), a sample size of 50 per group results in a power of 81% (nQuery Advisor 7.0).

Further scenarios assuming different response rates for tropifexor and the magnitude of effect added to tropifexor by CVC are described in [Table 3-1](#).

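### The stated efficacy power of 81% and 95% counts the placebo response twice; with the CVC effect that the protocol itself reports, it is about 14-19% and 35-44%

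*Protocol*

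**What the plan says.** Protocol section 9.8.2 and SAP section 3.2 take Week 48 fibrosis response rates of about 35% for CVC (F2/F3 patients, from the CENTAUR study) and 42% for tropifexor, which they label a best case. The combination rate is then built by addition. The protocol writes "75% of the efficacy for CVC will be added to the effect of tropifexor (i.e. a response rate of 69" (per cent). The SAP repeats that "75% of the efficacy for CVC will be added to the effect of tropifexor" and shows the sum as 42 + 0.75 × 35.

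Protocol Table 9-4 and SAP Table 3-1 do the same with one half, three quarters and all of the 35%, for tropifexor rates of 42%, 35% and 28%. The full-effect entries are 77%, 70% and 63%, which are 42 + 35, 35 + 35 and 28 + 35. For the 69% scenario, at 50 per arm and two-sided alpha 0.10 with a continuity-corrected test, both documents state 81% power against tropifexor and 95% against CVC.

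Protocol section 1.1 reports the Year 1 CENTAUR results for improvement of at least one fibrosis stage:

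- NASH CRN staging: "a higher proportion of participants in the CVC group (29%) compared with the combined placebo group (19" (per cent)
- with no worsening of steatohepatitis: "was met in twice as many subjects on CVC than placebo in the ITT population (20% vs 10" (per cent)
- Ishak staging: "Similarly, a higher proportion of participants in the CVC group (35%) compared with the combined" placebo group at 22%

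**The concern.** The quantity added as the effect of CVC is the whole proportion responding on CVC. Part of that proportion would have responded on placebo, and the same part is already inside tropifexor's rate. The sum is correct only if nobody responds on placebo. The protocol reports placebo responses of 10%, 19% and 22%.

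The fault runs through every row of both tables. The smallest increment, half of 35, is 17.5 points, already more than the largest full effect reported in section 1.1 (13 points). So no scenario, including the one labelled worst case, adds an effect as small as the evidence in the protocol.

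This matters because section 1.2 says "Data from this study will be used to evaluate whether further development of combination therapy with tropifexor + CVC" is worthwhile. A reader who trusts 81% and 95% would take a non-significant comparison as evidence that the combination adds little, when the trial would usually miss an effect of the reported size.

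**Working it through.** **Inputs.** From protocol 9.8.2 and SAP 3.2: n = 50 per arm; two-sided alpha 0.10 (z = 1.645), no multiplicity adjustment; tropifexor 42%, CVC 35%. From protocol 1.1, the effects of CVC over placebo: 29 − 19 = 10, 20 − 10 = 10 and 35 − 22 = 13 points.

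**Formula.** For rates p1 and p2, let d = |p1 − p2| and p̄ = (p1 + p2)/2. The continuity-corrected sample size is n′ = (nd − 1)²/(nd²), and

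power = Φ{ [d√n′ − 1.645 √(2p̄(1 − p̄))] / √(p1(1 − p1) + p2(1 − p2)) }.

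**Step 1: reproduce the plan.** For 69% against 42%: d = 0.27, n′ = 42.87, d√n′ = 1.768 and p̄ = 0.555. Power = Φ[(1.768 − 1.645 × 0.703)/0.676] = Φ(0.904) = 81.7% (stated 81%). For 69% against 35%: Φ(1.657) = 95.1% (stated 95%). Of the 18 power cells, 17 agree to within 1 point at the printed rates. The method therefore matches, and the fault lies in the rate put into it. The exception is the last cell, 63% against 35%: 84.0%, where both tables print 81%.

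**Step 2: the rounding.** 42 + 0.75 × 35 = 68.25, printed as 69. At 68.25% the power is 79.4% and 94.2%.

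**Step 3: add only the effect over placebo.** The plan's 42%, 35% and additive construction are kept.

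| CVC effect added | Combination rate | Power vs tropifexor 42% | Power vs CVC 35% |
|---|---|---|---|
| ¾ of 10 points | 42 + 7.5 = 49.5% | 13.7% | 35.1% |
| ¾ of 13 points | 42 + 9.75 = 51.75% | 19.1% | 43.7% |
| all of 10 points | 52% | 19.8% | 44.7% |
| all of 13 points | 55% | 29.1% | 56.7% |

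The stated values are 81% and 95% for three quarters, and 96% and 99% for the full effect. Exact binomial enumeration of the same test gives 13.0/33.9, 18.0/42.2, 18.6/43.2 and 27.5/55.0, so the approximation is not the cause.

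With the full 10-13 points added in the other tropifexor rows, power against tropifexor is 20.3-29.7% from 35% and 21.2-31.1% from 28%. The table states 96% for both.

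**Step 4: vary the placebo rate.** The F2/F3 placebo rate is not in the documents, so it is an assumption here. CVC stays at 35%, and the combination is 42 + 0.75 × (35 − placebo).

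| Assumed placebo rate | Combination rate | Power vs tropifexor | Power vs CVC |
|---|---|---|---|
| 0% | 68.25% | 79.4% | 94.2% |
| 10% | 60.75% | 51.2% | 77.6% |
| 15% | 57% | 36.4% | 64.5% |
| 19% | 54% | 25.8% | 52.7% |
| 22% | 51.75% | 19.1% | 43.7% |
| 25% | 49.5% | 13.7% | 35.1% |

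Of the rates tried, only 0% brings the stated power back.

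**Step 5: what the design can detect.** With tropifexor at 42% and 50 per arm, 80% power needs a difference of 26.4 points (26.8 by exact enumeration).

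**The case against.** The strongest objection is to the precision of 14-19% and 35-44%. The 10-13 point effects come from the whole CENTAUR population, while the 35% is described as an F2/F3 rate. Section 1.1 also says "Treatment benefits were greater in those with higher disease activity and fibrosis stage at baseline", so the F2/F3 effect may be larger. The 13-point figure is on the Ishak scale, whereas this trial uses NASH CRN, and one of the 10-point figures carries the extra steatohepatitis condition. With CVC at 35%, effects of 10-13 points imply a placebo rate of 22-25%, which neither document states. This stands. It is why step 4 gives a range and why any replacement power must be labelled as resting on an assumption. It does not rescue the stated figures: at a 10% placebo rate, power against tropifexor is still only 51%.

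The scale also matters. If three quarters of the same effects are applied as odds ratios to 42%, the combination rate is 52-57% and power is about 21-37% against tropifexor and 46-65% against CVC. With the full effect, power is about 32-56% and 60-81%. That departs from the plan's additive construction, and for the three-quarter scenario it remains far below 81% and 95%.

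It can also be said that 81% and 95% are right for the rates printed beside them, and that the assumptions are openly stated. True, but the best-case label is attached to tropifexor's 42% only, and neither document gives a reason for adding a gross rate.

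Finally, little in the design depends on this. Efficacy is secondary, the sample size rests on feasibility, and the protocol records enrolment as complete at 193 patients. That limits the remedy to a restatement. The two small slips are minor: the rounding moves power by 1-2 points, and the last cell errs by 3 points in the conservative direction.

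**Conclusion.** The concern holds. The combination rates add CVC's gross response rate as if it were its effect, so the stated power is too high. On the plan's own test, alpha and sample size, three quarters of the reported 10-13 point effect gives 14-19% against tropifexor and 35-44% against CVC. Even a fully additive CVC effect of that size would be missed against tropifexor about 71-80% of the time (100 − 29.1 and 100 − 19.8).

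The mechanism is certain, because the SAP prints the sum. The size rests on three assumptions: monotherapy rates of 42% and 35%, effects that add on the risk-difference scale, and whole-trial CVC effects standing in for F2/F3 patients. This is a wrong stated figure that should be corrected. It is not a reason to change the design.

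**What to change.** - Recalculate protocol 9.8.2 / Table 9-4 and SAP 3.2 / Table 3-1 with the combination rate equal to the tropifexor rate plus a fraction of CVC's placebo-adjusted effect. State the F2/F3 placebo rate as an assumption with a range, and give the power for each scenario.
- State that 50 per arm gives 80% power against tropifexor at 42% only for a difference of about 26-27 points.
- If the present scenario is kept for reference, label it as not placebo-adjusted, use 68.25% (power about 79% and 94%), and correct the 63% against 35% cell to 84%.
- Interpret the efficacy comparisons through the risk differences and odds ratios with 95% confidence intervals that are already planned.

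The cost is some wording and one recalculated table in each document, and the stated power becomes much less favourable. No patients are added, and the sample size, estimands, tests and analyses do not change.
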